# Sample size

In the pilot study we will recruit 96 participants, 48 in each arm, across the 4 sites. This will allow for exploration of key parameters needed to confirm sample size calculation for the efficacy study. It is sufficient to allow estimation of two-sided 95% Cl's around the proportions of eligible, consenting, adhering and followed-up at month 6 in each arm of the study with half-widths less than 0.15. It exceeds the 30 per group recommended by Lancaster et al (Lancaster et al., 2004) and the 35 per group recommended by Teare et al (Teare et al., 2014) for estimating the SE of a primary outcome with sufficient precision, including accounting for any variation across site, where 12 participants per arm per site is recommended.

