# Success criteria and/or targets

In the pilot phase of the study we will estimate likely proportions of participants who are eligible, who consent, adhere to the intervention and the proportion followed-up at 6 months. Proportions will be compared to predefined progression criteria.

Criteria			
Proportion referred who are eligible	70%	50%	40%
Proportion eligible who consent	70%	50%	40%
Proportion eligible who adhere		60%	40%
Proportion followed-up (secondary)		70%	60%

Where progression criteria are green the efficacy study will continue as planned, if amber or red discussion regarding remedial action will be taken prior to embarking on the efficacy study.

In addition to proportions we will assess data completeness for each outcome instrument. A threshold of 60% complete will be used to assess whether an outcome instrument should be included in the efficacy trial.

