# Randomisation

Randomisation will employ random permuted blocks of variable size stratified by site; Kent, Cornwall, Sefton, Lancashire and by age group; 10-14 versus 15-17 years. Random strings will be created for each stratification combination and deployed independent of the research team and each participant will have equal probability of being allocated to the intervention or business as usual.

Randomisation will be conducted after eligibility has been assessed, informed consent provided and baseline assessment conducted. The researcher will enter necessary details into an encrypted database and after necessary data has been checked an allocation code will be provided. This code will indicate the nature of allocated group. The researcher will not be able to access randomisation codes. The participant will not be blind to the intervention.

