# Methods and data collection

# Quantitative data collection

Baseline quantitative outcomes, detailed below, will be collected after eligibility has been assessed and consent provided. Assessment will be conducted on-line using a questionnaire designed for on-line completion and tested with peers of a similar age. The researcher will support the participant in the completion of the baseline outcomes and be on hand to answer any questions and ameliorate any difficulties. The participant will be allocated immediately after the baseline assessment has been completed.

Participants allocated to the intervention group will be asked to complete the treatment alliance outcomes after the second session. Participants will be contacted at six months after allocation and will complete the follow-up outcomes. Follow-up outcomes will be collected on-line and the young person will be supported in completion by a researcher.

Eligible young people are referred to WAWU at the participating sites

WAWU provide information sheet and check whether the young person is willing to consent to the trial

> If no consent young person receives TAU delivered by WAWU

If informed consent is provided research staff contact the young person and conduct the baseline assessment and young person randomised

Randomised to the REFRAME intervention

Receives session 1 Drug Grid

Receives session 2 Drug Triangle

Completes month 6 follow-up

Randomised to TAU

Receives TAU one session of advice, information and signposting currently delivered to this population

Completes month 6 follow-up

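### The per-arm precision claim covers eligibility and consent, which are settled before randomisation, and the progression table counts adherence among the eligible rather than those randomised

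*Protocol*

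**What the plan says.** The Sample size section states that "we will recruit 96 participants, 48 in each arm, across the 4 sites". It then claims that this number supports two-sided 95% confidence intervals around the "proportions of eligible, consenting, adhering and followed-up at month 6 in each arm of the study with half-widths less than 0.15". The same section also supports the number with two published per-group pilot recommendations (30 and 35) and with 12 participants per arm per site.

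The Randomisation section fixes the order of events: "Randomisation will be conducted after eligibility has been assessed, informed consent provided and baseline assessment conducted". The participant flow under Quantitative data collection agrees, and adds what happens to those who decline: "If no consent young person receives TAU delivered by WAWU". They are not allocated.

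The table under Success criteria and/or targets defines the first two criteria as "Proportion referred who are eligible" and "Proportion eligible who consent", each with cut-points of 70%, 50% and 40%. Its adherence row is also expressed as a proportion of the eligible, with printed cut-points of 60% and 40%. The follow-up row (70% and 60%) names no denominator.

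**The concern.** The precision sentence treats four proportions alike and attaches one per-arm bound to all of them. Two of the four are screening quantities. Everyone in an arm has already been found eligible and has consented, so a per-arm value for either would be 100% by design and carry no information.

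These four proportions are also the progression criteria, so the reader needs to know what each is a proportion of and how precisely it will be known. A reader who carried the stated margin over to consent would see more uncertainty than the pilot will have.

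The adherence row has the opposite problem. A per-arm precision is claimed for it, but the progression table gives it a denominator that includes young people who have no arm. That affects the value of the criterion itself, not only its margin.

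**Working it through.** **Inputs.** 96 randomised, 48 per arm, two-sided 95% (Sample size). Equal allocation (Randomisation). Cut-points of 70%, 50% and 40% for eligibility and consent, and 60% and 40% for adherence (Success criteria and/or targets). An 80% recruitment rate in earlier work (Risks, item 3), used only as a scenario. The protocol gives no expected number referred or eligible, so those counts are derived below. They assume that everyone who consents is randomised.

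**1. The plan's own figure.** Half-width = 1.96 × √(p(1 − p)/n). With n = 48:
- p = 0.5: 1.96 × √(0.25/48) = 0.141
- p = 0.7: 1.96 × √(0.21/48) = 0.130

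At p = 0.5 the Wilson interval gives 0.136 and Clopper-Pearson 0.148. Only the continuity-corrected Wald interval goes slightly over, at 0.152. The bound of 0.15 therefore reproduces, for a proportion of the 48 people in an arm.

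**2. Eligibility and consent on their own denominators.** Number eligible = 96 / consent rate. Number referred = number eligible / eligibility rate.

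| Eligible / consent rate | Eligible | Referred | Half-width, consent | Half-width, eligibility |
|---|---|---|---|---|
| 70% / 70% | about 137 | about 196 | 0.077 | 0.064 |
| 50% / 50% | 192 | 384 | 0.071 | 0.050 |
| 40% / 40% | 240 | 600 | 0.062 | 0.039 |
| 70% / 80% | 120 | 172 | 0.072 | 0.069 |

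**3. Upper limit.** Putting n = 96/p into the formula gives a consent half-width of 1.96 × √(p²(1 − p)/96). This is largest at p = 2/3, where p²(1 − p) = 4/27, giving 1.96 × √(0.1481/96) = 0.077. The same limit holds for eligibility, because at least 96 people must be eligible. So 0.15 is about twice the largest margin possible: 0.15/0.077 = 1.95.

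**4. What the difference looks like.** Suppose 60% of the eligible consent, so that 96/0.6 = 160 are eligible. The margin is 1.96 × √(0.24/160) = 0.076, an interval of about 52% to 68%, which lies between the 50% and 70% cut-points. With the n = 48 margin of 0.139 it would appear as about 46% to 74%, spanning both.

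**5. Adherence as the progression table defines it.** If adherence means attending the intervention, at most 48 people can adhere, so the ceiling is 48 / number eligible, which is half the consent rate:
- 50% consent: 48/192 = 25%
- 70% consent: 48/137 = 35%
- 80% consent: 48/120 = 40%
- 100% consent: 48/96 = 50%

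Even with perfect attendance, the 60% cut-point is out of reach at any consent rate, and the 40% cut-point is out of reach below 80% consent. If attendance in both arms counts (Outcome measures records both), the ceiling is the consent rate itself, for example 96/137 = 70%.

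**6. Adherence and follow-up among those randomised.** Adherence in the intervention arm (n = 48): 0.139 at 60% or 40%, and at most 0.141. Follow-up at 70%: 0.130 per arm and 1.96 × √(0.21/96) = 0.092 pooled. At 50%: 0.141 and 0.100.

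**The case against.** The best defence is that the protocol states a ceiling, and the ceiling holds. Half-widths of 0.064 and 0.077 are below 0.15, so no arithmetic fails. That stands. A reader might infer that the stated precision is wrong by a factor of two, but the text gives an upper bound and all four proportions meet it.

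A reader might also infer that eligibility and consent have no denominator at all. The documents do not support that either: the progression table names pooled ones, the referred and the eligible. What they lack is a per-arm denominator.

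The per-arm qualifier could be read as attaching only to the last items in the list. The grammar allows this, but the sentence then gives no denominator or expected count for the first two.

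It can also be said that no decision turns on 0.15, since the table compares observed proportions with cut-points and states no interval rule. That is fair, and it limits the harm from the precision sentence. It does not answer the adherence point, because there the denominator changes the observed proportion that is compared with the cut-points.

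**Conclusion.** The concern holds as a denominator error in two places. First, the Sample size section claims per-arm precision for two proportions that exist only before randomisation. For these the bound is true but about twice the largest actual margin (0.077). Second, the progression table's adherence row conflicts with that section's per-arm precision. Read as intervention adherence, it would be capped at 35% at 70% consent, below the lowest printed cut-point of 40%.

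It would be a mistake to conclude that 96 is too few or unjustified. The bound fits adherence and follow-up per arm, and the number also rests on the published recommendations and the per-site count (12 × 2 arms × 4 sites = 96).

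The referred and eligible counts are scenarios built on the protocol's own cut-points. If some who consent are not randomised, both denominators grow and the intervention-adherence ceiling falls further. The 35% figure depends on adherence meaning the intervention arm. The protocol does not say so outright, but its logic model sets its engagement target among those offered the intervention.

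**What to change.** - **Sample size:** limit the per-arm bound to adherence and follow-up among the 48 randomised per arm (at most about 0.14), with follow-up also given pooled over 96 (about 0.10).
- **Sample size:** give pooled precision for eligibility (of all referred) and consent (of all eligible) as a range under stated assumptions. For example, at 70%/70%, about 196 referred (0.064) and about 137 eligible (0.077); at 50%/50%, 0.050 and 0.071. Label the counts as assumptions.
- **Success criteria and/or targets:** change the adherence denominator from the eligible to those randomised, say whether the criterion concerns the intervention arm (n = 48), and state that follow-up is among all randomised.

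The cost is a wording change, entered in the version history after the discussion with the funder and developer that the protocol requires. It needs no extra participants or data, because the referral and eligibility counts are already needed for the first two criteria.

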# Methods and data collection

# Quantitative data collection

Baseline quantitative outcomes, detailed below, will be collected after eligibility has been assessed and consent provided. Assessment will be conducted on-line using a questionnaire designed for on-line completion and tested with peers of a similar age. The researcher will support the participant in the completion of the baseline outcomes and be on hand to answer any questions and ameliorate any difficulties. The participant will be allocated immediately after the baseline assessment has been completed.

Participants allocated to the intervention group will be asked to complete the treatment alliance outcomes after the second session. Participants will be contacted at six months after allocation and will complete the follow-up outcomes. Follow-up outcomes will be collected on-line and the young person will be supported in completion by a researcher.

Eligible young people are referred to WAWU at the participating sites

WAWU provide information sheet and check whether the young person is willing to consent to the trial

> If no consent young person receives TAU delivered by WAWU

If informed consent is provided research staff contact the young person and conduct the baseline assessment and young person randomised

Randomised to the REFRAME intervention

Receives session 1 Drug Grid

Receives session 2 Drug Triangle

Completes month 6 follow-up

Randomised to TAU

Receives TAU one session of advice, information and signposting currently delivered to this population

Completes month 6 follow-up

# Qualitative data collection

To address these research questions in depth, the qualitative aspect of the work will involve the collection of narrative accounts from a range of individuals using semi-structured interviews. These will be collected from young people participating and those who withdraw, and staff involved in the programme delivery. Professionals and young people will be sampled purposefully, and young people will be approached for participation within six weeks of completing the intervention.

The qualitative component of the study will be purposive and include interviews with participants, intervention staff and police. Participants will be chosen purposively to provide diversity in terms of site, and age and ensure appropriate participation by gender, social class, and ethnicity. The sample size considerations of the qualitative component are driven by the need to achieve data saturation, and this needs to be judged in practice rather than stated a priori.

Key questions addressed by the qualitative component will both be informed by, and inform, elements of the quantitative analysis, they include:

- Do participants, providers and police perceive any external or logistical issues as impacting referral, intervention delivery, attrition, or study assessments?
- What are participants' positive and negative intervention experiences and how do these fit with providers' perceptions? At what points in the intervention are these most likely?
- What reasons do participants offer for their misuse and for their intervention responses?
- Can practices associated with the intervention be amended to increase its acceptability and impact?
- Do police perceive the intervention as impacting participants' offending?

To explore beyond the realms of the research project itself, we will also conduct a number of qualitative focus groups with key stakeholders not involved in the study itself. These groups will comprise 6 to 8 individuals and will be repeated until data saturation is reached. This purposive sample will be guided by the findings of the survey of practice across the country and include areas of low/ high activity, capacity, and depravation. These focus

groups will explore views on organisational capacity, intervention delivery, eligibility, referral mechanisms, the optimum number of standardised measures required to monitor intervention delivery, minimum standards of experience for interventionists, delivery of training and ongoing supervision. These focus groups will allow us to develop a set of minimum standards, standard operating procedures for training and intervention delivery and a training and an intervention delivery manual.

In addition to these focus groups, we will individually interview purposefully selected children and young people from across the country who meet the same criteria as the intervention participants but who have not received any intervention. Again, the purposive sample will be guided by diversity criteria (i.e., areas of low/high deprivation, age, gender, social class, and ethnicity). Participants will be asked to provide views on how their substance misuse has been handled and what might aid them/have aided them in reducing it as well as any involvement in non-violent offences. As with all the qualitative research in this project, sample size will be determined according to data saturation rather than a priori

# **Data analysis**

In the pilot phase of the study we will estimate likely proportions of participants who are eligible, who consent and the proportion followed-up at 6 months. Each of these will be assessed against progression criteria agreed a priori.

We will conduct a descriptive analysis of outcomes including measures of central tendency and estimates of precision for continuous outcomes and proportions for categorical outcomes. Inferential analysis at the pilot stage will focus on the primary outcome, offences at 6-months with the aim of providing estimates of the potential effect of the intervention. After conducting diagnostic plots and selecting an appropriate regression approach, adjusting for baseline values and stratification variables as covariates, we will present the marginal effect, mean difference between the intervention and control groups and 80% confidence intervals. This analysis will allow us to confirm or revise our sample size calculation. At this stage we will also explore the pattern of missing data for each outcome and by key demographic indicators such as ethnicity and age, if missing data exceeds 40%, we will make judgements about whether to incorporate the outcome in the efficacy study.

# **Outputs**

The main outputs of the pilot trial will be twofold

- 1. A full report on the design, conduct, analysis and interpretation of progression to an efficacy trial.
- 2. If an efficacy trial is warranted a revised protocol for the design of that trial.

# **Ethics and registration**

Ethics has been provided by an independent ethics committee, University of Kent Social Science Research Ethics Committee Ref SRC0498. The trial will be registered in the ISRTN trial registry and www.controlled-trials.com.

# **Data protection**

All systems and personnel are approved for the management of clinical and sensitive data and are ISO certified to ISO27001 standard. This includes all physical systems, systems to detect intrusion, encryption of data from point of collection to storage, quality assurance and audit trails associated with any data collected. All identifiable data collected will be done with explicit consent and limited to data to allow participants to be contacted for follow-up. Data linkage will employ a unique identifier where the link to identifiable information will be stored on an encrypted secure database. Researchers will be trained to GCP standard and will comply with all relevant data protection legislation. Once final followup is completed, personally identifiable information will be deleted from the dataset held by the university and where consent has been granted encrypted data will be transferred to the Youth Endowment Fund data archive. Data collection and management will be governed by a trial specific Standard Operating Procedure agreed and approved by ethics.

# **Risks**

Our experience of similar studies has enabled us to develop and pilot several risk mitigations strategies. We have identified the following key risks

1. Lack of engagement by stakeholders **(LOW)**. We plan on actively engaging with all stakeholders to ensure the importance of the project is recognised. We aim to visit all sites early on and plan on engaging with staff at all levels in the partner organisations.

2. Potential contamination **(LOW)**. As a randomised controlled trial, the potential for contamination is low. The design of the standardised control group, delivered by staff not involved in delivering the intervention, will address any potential for contamination. All follow-ups will be conducted blind to baseline allocation.

3. Poor recruitment **(MEDIUM)**. We have extensive experience of working with marginalised populations. In addition to clear referral and recruitment strategies we will ensure

recruitment is constantly monitored to identify emerging issues, reduce barriers to participation by using few inclusion criteria and minimising exclusion criteria, providing clear information, and ensuring participants are clear on what the trial entails. Our previous experience with a similar population recruited 80% of those participants considered potentially eligible.

4. Poor adherence to follow-up **(MEDIUM)**. As our primary outcome measure is not participant assessed this issue relates in the main to the collection of secondary and process measures. In our previous studies with similar populations we have met, and exceeded, our target follow-up rate of 70% at 6-months. We have developed several follow-up strategies including multiple contact details, details of contactable others and ensuring participants are recompensed for the time spent engaging in follow-up assessments.

5. Failure to access PNC data **(MEDIUM)**. The PNC data constitutes the primary outcome. We will ensure data sharing agreements with local police forces are in place at the start of the pilot phase of the study. We will ensure consent is provided to access this data and this has been reviewed by the police data controller and ethics. If necessary, we will implement alternative sources for this data using self-report.

6. latrogenic and adverse events **(LOW)**. We do not anticipate any iatrogenic effects and brief interventions are not usually associated with adverse events. We will monitor any iatrogenic or adverse events and create a reporting system. Any event that is potentially a consequence of the trial will be reviewed by the trial management group and where appropriate an independent committee, who will decide regarding continued conduct of the trial.

7. Ongoing COVID restrictions **(LOW)**. The trial recruitment and intervention will be conducted in accordance with government and provider guidelines on working with COVID. Follow-ups will be conducted remotely using video technology to reduce both the burden on participants and contact between research staff and multiple participants.

# Timeline

Dates	Activity	Staff responsible/ leading
12/01/22	Study start-up meeting with we Are with You Draft pilot protocol submitted to YEF Draft analysis plan submitted to YEF Draft consent form delivered to YEF Draft information sheet delivered to YEF Ethics application submitted Data sharing agreements Data management and randomisation systems developed and piloted	[name]
31/01/22	Site staff training complete PNC data sharing agreements organised	[name]
31/01/22	Final pilot protocol delivered to YEF Final pilot analysis plan delivered to YEF Final consent form delivered to YEF Final information sheet delivered to YEF	[name]
31/05/22	Complete recruitment of 96 participants	[name]
31/10/22	Complete quantitative outcomes at 6 months for 96 participants	[name]
31/10/22	Schedule and conduct qualitative interviews	[name]/ [name]
31/10/22	Progression recommendation made	[name]
31/12/22	Conduct interim analysis Revise and submit efficacy study protocol Submit draft pilot evaluation report Revises information and privacy notices and seeks YEF approval	[name]
29/04/23	Submit final evaluation report	[name]

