# **Outcome measures**

Our primary outcome is all offences; including arrests, cautions and charges, 6-months post randomisation obtained directly from the Police National Computer. In addition to the primary outcome this will allow us to extract data for the period 6 months prior to randomisation as a covariate and other outcomes including all offences and specific substance use offences as secondary outcomes. Frequency of substance use will be assessed at 6-months using the Time Line Follow Back Method (TLFB; (Levy et al., 2004; Sobell and Sobell, 1995)), a valid and reliable tool for assessing the frequency and quantity of substance use over time periods ranging from 1 to 365 days and validated specifically for adolescents (Levy et al., 2004). To minimise burden, we will use the 28-day version which takes about 10 minutes to complete and demonstrates an excellent level of agreement with longer versions. This tool allows us to derive the percent days abstinent from substance use and allows derivation of several other outcomes over the period (e.g., quantity and type of substances consumed). As there is evidence of assessment reactivity associated with TLFB in brief intervention studies we will only measure TLFB at 6-months and employ a single frequency of substance use question at baseline for inclusion in the analytical model as a covariate.

Mental health and wellbeing will be assessed using the Warwick-Edinburgh Mental Wellbeing scale (WEMWBS; (Clarke et al., 2011)). WEMWBS is a 14-item, self-completed scale addressing different aspects of eudemonic and hedonic mental health wellbeing. Healthrelated quality of life will be derived from a short assessment of health utility used extensively in this population (CHU-9D; (Stevens, 2012)).

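### Six-month outcomes for all 96 participants, and the progression recommendation, are dated five months after recruitment closes, so the follow-up criterion cannot be evaluated on all 96 by then

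*Protocol*

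**What the plan says.** The Timeline table in the Protocol gives these dates:

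- 31/05/22: "Complete recruitment of 96 participants"
- 31/10/22: "Complete quantitative outcomes at 6 months for 96 participants"
- 31/10/22: "Progression recommendation made"
- 31/12/22: "Conduct interim analysis", in the same row as the revised efficacy protocol and the draft pilot report
- 29/04/23: final evaluation report

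The section on quantitative data collection fixes both ends of the follow-up interval. Its start: "The participant will be allocated immediately after the baseline assessment has been completed". Its end: "Participants will be contacted at six months after allocation and will complete the follow-up outcomes". The primary outcome has the same length but comes from police records: "Our primary outcome is all offences; including arrests, cautions and charges, 6-months post randomisation obtained directly from the Police National Computer" (Outcome measures).

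The section on success criteria compares four proportions with preset thresholds. The fourth is the row beginning "Proportion followed-up (secondary", for which the available text shows 70% and 60%. The Sample size section says that 48 per arm gives two-sided 95% confidence intervals with half-widths below 0.15 for each of these proportions, including month-6 follow-up.

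**The concern.** Recruitment ends five months before six-month follow-up is meant to be complete for everyone. The dates cannot all hold: either the latest recruits are assessed early, or they are missing when the recommendation is made. The Protocol gives no early visit window, no data cut, and no rule for basing the follow-up proportion on a subset.

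What is at stake is one of the four progression criteria. On the recommendation date, a low share of the 96 could reflect the calendar rather than retention, and the denominator for reporting it is undefined. The recommendation is also dated two months before the only scheduled analysis, although the Data analysis section is where the Protocol places the assessment of these proportions.

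**Working it through.** **1. The dates (no assumption needed).**
- Last allocation 31/05/22 plus six months = 30/11/22, which is 183 days.
- Time actually allowed, 31/05/22 to 31/10/22 = 153 days, or five calendar months.
- Shortfall = 183 − 153 = 30 days.
- To be due by 31/10/22, a participant must be allocated by about 30/04/22. All 31 days of May fall outside.

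**2. The plan's own precision figure.** Half-width = 1.96 × √(p(1 − p)/n). With n = 48 per arm:
- p = 0.5: 0.141
- p = 0.6: 0.139
- p = 0.7: 0.130

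The stated figure of below 0.15 is reproduced. At p = 0.5 it requires n ≥ 1.96² × 0.25 / 0.15² = 42.7, so 43 per arm.

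**3. How many are not yet due on 31/10/22 (assumption: even accrual from an assumed start).** The Protocol gives no recruitment start. Three are used: 31/01/22 (site training complete, Timeline), 10/02/22 (protocol version date) and 01/03/22 (an arbitrary later start).
- Not due = 96 × 31 / (days from start to 31/05/22)
- Ceiling on follow-up of the 96 = 1 − 31/days
- Due per arm = (96 − not due)/2
- Half-width as in step 2, at p = 0.5

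| Assumed start | Days | Not due on 31/10/22 | Ceiling | Due per arm | Worst-case half-width |
|---|---|---|---|---|---|
| 31/01/22 | 120 | 24.8 | 74.2% | 35.6 | 0.164 |
| 10/02/22 | 110 | 27.1 | 71.8% | 34.5 | 0.167 |
| 01/03/22 | 91 | 32.7 | 65.9% | 31.6 | 0.174 |

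The ceiling assumes no loss at all. A later start or back-loaded recruitment makes it lower; front-loaded recruitment makes it higher.

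**4. What each denominator would do.**
- *All 96, with those not due counted as not followed up.* At the 70% follow-up target in the Risks section, the observed share would be 0.70 × 74.2% = 51.9%, 0.70 × 71.8% = 50.3%, or 0.70 × 65.9% = 46.2%. All are below 60%, the lower threshold shown.
- *Only those already due.* This removes the artefact, but 32 to 36 per arm is short of the 43 needed. The group left out is also, by construction, the latest recruits.

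**The case against.** **The primary outcome.** A reader might infer that the police-record outcome is cut short for May recruits. The Protocol does not establish this. Those data need no visit, the Timeline gives no separate extraction date, and the last six-month window closes on 30/11/22, a month before the analysis row. Truncation would follow only if the extract were taken on 31/10/22.

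**A misleading stop decision.** A reader might also infer that good retention would be misread and the efficacy trial halted. That goes too far. The success criteria section says that amber or red leads to discussion of remedial action, not an automatic stop. The low rates in step 4 arise only if participants not yet due are counted as lost. No section says to do that, and the team would know who was not due.

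**The order of recommendation and analysis.** Progression rests on operational proportions, three of which need no six-month data. The offence-effect analysis serves the sample size calculation, which fits its place beside the efficacy protocol revision. No section makes the recommendation wait for it. This stands in part: the follow-up proportion does need the six-month data, and the Protocol lists its assessment under Data analysis.

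**The counts.** They depend on assumed start dates and even accrual. With an assumed 14-day early tolerance, which the Protocol does not give, and a 31/01/22 start, only 17/120 = 14% would not be due. This objection also stands, so the counts are a range and not a forecast.

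None of this removes the 30-day conflict, which no other section reconciles.

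**Conclusion.** The concern holds in limited form. Certain, from the Protocol's own dates: six-month outcomes for all 96 cannot be complete on 31/10/22 if recruitment runs to 31/05/22, and the recommendation is dated before both full follow-up and the scheduled analysis. The follow-up criterion therefore cannot be evaluated on all 96 when the recommendation is made.

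Conditional on even accrual from a start between 31/01/22 and 01/03/22: about 25 to 33 of 96 would not be due, capping follow-up of the 96 at about 66% to 74%. Restricting to those due gives an undistorted rate but misses the stated precision.

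The eligibility, consent and adherence criteria are not affected. The documents support neither a truncated primary outcome nor an automatic wrong decision. If recruitment in fact finished by about 30/04/22 the conflict would disappear, but that is not what the plan says.

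**What to change.** Amend the Timeline as follows:

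1. Date completion of the six-month outcomes no earlier than 30/11/22 plus any visit window, and state that window.
2. State that police-record data are extracted only after each participant's full six-month window has closed.
3. Date the progression recommendation after the follow-up proportion has been computed on all 96.
4. Check the milestones for the efficacy protocol revision and draft report, both due 31/12/22, and move them if the later recommendation leaves too little time.

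The final report date of 29/04/23 can stand. The cost is a recommendation one to two months later and possible pressure on the 31/12/22 deliverables.

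If 31/10/22 cannot move, the alternatives are to close recruitment by about 30/04/22, or to define the follow-up proportion among those already due. The second would require the Sample size section to concede a worst-case half-width of about 0.164 to 0.174 under the accrual assumptions above, so it is the weaker choice.
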